4. SELECTION AND ENROLLMENT OF PARTICIPANTS

According to the most recent statistics from the U.S. National Health Interview Survey (NHIS), when collapsing across gender, approximately 29.2% of Whites, 27.2.0% of Blacks/African Americans, and 27.4% of Hispanics reported low back pain in the previous three months. These data, shown in the table below are adapted from the Summary Health Statistics for U.S. Adults: National Health Interview Survey published in 2012. Although these national statistics indicate that low back pain is slightly more common amongst Whites as compared to African Americans and Hispanics, we will recruit our sample to ensure that it meets or exceeds the proportion of ethnic and racial minorities in the population according to 2010 U.S. Census figures. Specifically, we plan to enroll 16% Hispanic and 84% Non-Hispanic participants as well as 73% White, 17% African American, 7% Asian American, 2% American Indian/Alaskan Native, and 1% Native Hawaiian or Other Pacific Islander.

Planned Inclusion Enrollment

Racial Categories	Ethnic Categories				Total	
	Not Hispanic or Latino		Hispanic or Latino			
	Female	Male	Female	Male		
American Indian or Alaska Native	1	1	0	0	2	
Asian	8	8	0	0	16	
Native	1	1	0	0	2	

Hawaiian or Other Pacific Islander					
Black or African American	16	16	4	3	39
White	71	70	15	15	171
More than One Race	0	0	0	0	0
Unknown or Not Reported	0	0	0	0	0
Total	97	96	19	18	230

Using recruitment procedures that we have successfully employed in prior CLBP trials (R01 AT00697, R21AR064430, R21AR063909) as well as prior cohort studies,^{18, 35, 45-48} we will recruit 230 participants with CLBP and fear of movement. We will include participants with CLBP between the ages of 18-60 and who report no health condition(s) that may restrict movement or preclude safe participation. Participants will be recruited through advertisements and flyers posted in the local community, and via a combination of electronic, radio, print, and possibly television announcements in the local and surrounding communities. We may also recruit from local clinics. Finally, ResearchMatch.org will be used as a recruitment tool for this protocol. ResearchMatch.org is a national electronic, web-based recruitment tool that was created through the Clinical & Translational Science Awards Consortium in 2009 and is maintained at Vanderbilt University as an IRB-approved data repository (see IRB #090207).

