9.2 Sample Size and Randomization

We will recruit 230 participants with chronic low back pain (CLBP) and fear of movement. We will include participants with CLBP between the ages of 18-60 and who report no health condition(s) that may restrict movement or preclude safe participation. Participants will be recruited from the general population and specific

organizations such as Virginia Commonwealth University's University Medical Associates.

Aim 1: Power analyses were conducted to determine the sample size needed to achieve clinically important differences in our co-primary clinical outcome measures of pain and disability. Based on the extant literature, we based our analyses on a \geq 30% decrease in pain ratings¹ (on the 0-10 NRS scale) and a 30% decrease in disability ratings on the RMDQ² in the experimental group. Further, we predict a 10% decrease in pain and disability in the control group to account for potential placebo effects. The population standard deviations were set at 75% of the population mean values. The pre-post correlation was estimated as $r=0.7$. These population parameters translate into an effect size of $f=0.30$. Using these parameters, we drew 10,000 samples from a normal population distribution. Based on these parameters, to achieve power of 80% and $\alpha=0.05$ will require a total $N=78$.

Aim 2 & 3: Power analyses were conducted to determine the sample size needed to address hypotheses 2.1, 2.2, and 3. Using the method described by Morris (2008),³ we calculated effect size estimates from randomized clinical trials on the effects of graded activity or graded exposure interventions on changes in disability among individuals with CLBP.⁴⁻⁷ For our power analyses, we adopted the median estimated effect size: $\delta = .45$, which corresponds to what would commonly be described as a medium effect size. Following Raudenbush and Liu's (2000) recommendation,⁸ we set the residual error variance to 1 and estimated the between-subject slope variance to be 0.30. For power equal to .80 and $\alpha=0.05$, a sample size of 209 participants was indicated.

Based on the sample size calculations, using a sex-stratified random allocation table, we need a minimum sample of 209 participants to address Aims 1-3. To allow for 10% attrition from baseline to 48-week follow-up, we will recruit 230 participants.

Treatment Assignment Procedures

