Randomization & Stratification: The study statistician will use the R statistical language to block randomize treatments stratified by sex. Then the study coordinator will assign subjects to the treatment arms.

Masking or Blinding: The principal investigators, the statistician, and members of the data collection team will remain blinded to intervention assignment throughout the duration of the study. They will be given the identifying codes only at the end of the study when it is necessary to interpret the results. The un-blinded study coordinator, who is responsible for scheduling testing and treatment sessions, will serve to receive the study patients and escort them to the various testing and treatments sites to minimize the interaction between patients; however, the study coordinator will not participate in the assessments.

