9.6 Data Analyses

We will analyze all outcome variables (pain, disability, pain/harm expectancy, and lumbar flexion) using linear mixed-effects (LME) models with treatment (Experimental, Control) as a between-subject fixed effect and time (pre-treatment, 1, 6, 12, 24, and 48 weeks) as a within-subject fixed effect. Given the expected findings, both linear and quadratic time effects will be tested in every model. We will also include demographic covariates (e.g., age, BMI) and potential confounders (e.g., radiating versus non radiating pain) as well as sex stratification in the LME models. Any variables that differ at baseline will be included in the statistical models as potential confounders.

Intention-to-treat analyses are commonly conducted to analyze randomized clinical trial data in the presence of missing values. While various imputation strategies have been proposed to estimate missing data, such as last observation carried forward, use of LME models to analyze longitudinal data renders these strategies largely unnecessary. We will also conduct equivalent per-protocol analyses that will include only successfully adhered participants (i.e., attending $\geq 70\%$ of gaming sessions).

Aim 1. Examine immediate clinical outcomes as a function of treatment. Relative to

the control group, participants in the experimental group will show greater reductions in pain and disability at post-treatment relative to pre-treatment baseline (Hypothesis 1).

To test Hypothesis 1, we will examine the Treatment by Time (baseline-post treatment) interaction in a LME model: a greater reduction in pain and disability in the experimental group than in the control group.

Aim 2. Examine potential mechanisms of pre- to post-treatment changes in clinical outcomes. Participants in the experimental group will exhibit greater pre- to post-treatment decreases in pain/harm expectancy and increases in lumbar flexion as compared to the control group (Hypothesis 2.1). Decreases in pain/harm expectancy and increases in lumbar flexion will be positively related to pre- to post-treatment reductions in pain and disability (Hypothesis 2.2).

Aim 3. Examine maintenance of treatment gains at 1-, 6-, 12-, 24-, and 48-weeks post-treatment. Relative to the control group, participants in the experimental group will continue to show lower levels of pain and disability at each time point as well as increased activity in their natural environment (Hypothesis 3).

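### Recruiting 230 covers about 9% attrition, not the stated 10%: a 10% loss leaves 207, two below the plan's own minimum of 209

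*Combined protocol and SAP*

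**What the plan says.** Section 9.2 (Sample Size and Randomization) reports two power calculations. The one for Aim 1 gives a total of 78. The one for Aims 2 and 3 concludes: "For power equal to .80 and $\alpha=0.05$, a sample size of 209 participants was indicated". The larger figure becomes the overall requirement: "we need a minimum sample of 209 participants to address Aims 1-3". The next sentence sets the recruitment target: "To allow for 10% attrition from baseline to 48-week follow-up, we will recruit 230 participants".

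The synopsis, under Sample Size and Population, repeats this text. Section 4 carries the same target ("we will recruit 230 participants with CLBP and fear of movement"), and its planned enrolment table totals 230. The attrition allowance is not defined in any other way elsewhere in the document.

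**The concern.** Attrition between baseline and week 48 is a share of those who enter the trial. A target that allows for 10% attrition should therefore leave at least the stated minimum once 10% of those recruited have been lost. Here it does not, so the minimum, the attrition rate and the target cannot all hold.

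This sentence is the plan's only justification for its recruitment target. Any reader can check it in one line, and it would pass into any report that quotes the sample-size rationale. What is at stake is the accuracy of a stated planning figure; the design and the analysis are unaffected.

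**Working it through.** **Inputs from section 9.2.** Minimum sample n = 209; attrition d = 0.10; target 230.

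**1. Reproduce the plan's figure.** n x (1 + d) = 209 x 1.10 = 229.9, which rounds up to 230. This matches exactly and shows how the target was obtained.

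**2. Apply the stated attrition to the target.** 230 x (1 - 0.10) = 207. The shortfall is 209 - 207 = 2 participants at week 48.

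**3. Find what 230 does allow for.** 230 - 209 = 21 losses, and 21/230 = 9.1%.

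**4. Find the number that a 10% allowance needs.** n / (1 - d) = 209/0.90 = 232.2, rounded up to 233. Check: 233 x 0.90 = 209.7, which meets 209; 232 x 0.90 = 208.8, which does not. The target is 3 recruits short, and 3/233 = 1.3%.

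Steps 1 to 4 use only figures in the document.

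**5. Size of the effect on power (a reconstruction).** Section 9.2 gives a standardised effect of 0.45 for Aims 2 and 3, and says of the variances: "we set the residual error variance to 1 and estimated the between-subject slope variance to be 0.30". It does not state the number or spacing of time points, the sidedness of the test or the allocation ratio (the randomisation text says only "block randomize treatments stratified by sex"). I assumed five equally spaced time points, a two-sided test and 1:1 allocation.

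- Sampling variance of one participant's slope: V = 1 / (sum of squared centred times) = 1/(4 + 1 + 0 + 1 + 4) = 0.10.
- Noncentrality: lambda = N x 0.45² x 0.30 / [4 x (0.30 + 0.10)] = N x 0.06075/1.6.
- Test: F with 1 and N - 2 degrees of freedom at the 5% level.

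| N with complete data | lambda | Power |
|---|---|---|
| 207 | 7.86 | 79.7% |
| 208 | 7.90 | 79.9% |
| 209 | 7.94 | 80.1% |
| 230 | 8.73 | 83.7% |

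Under these assumptions 209 is the smallest N that reaches 80%, which agrees with the plan. The match supports the reconstruction but does not prove it: six equally spaced points would give 187, and the actual visits are unequally spaced.

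A check that needs no time-point assumption takes power as exactly 80% at 209 and lets the normal test statistic scale with the square root of N. At 207, power is Φ[(1.960 + 0.842) x √(207/209) - 1.960] = 79.6%. Either way, two fewer complete participants cost about 0.4 percentage points.

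**The case against.** The strongest reply is that the slip has no practical consequence. Several parts of that reply stand.

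- **Partial data are kept.** Section 9.3 includes every randomised participant with baseline assessments in the primary intention-to-treat analysis, and section 9.6 analyses the repeated measures with linear mixed-effects models. Someone lost after week 12 still contributes the earlier visits. The 207 who remain at week 48 are not the analysed sample.
- **The co-primary comparison is not where the allowance applies.** Hypothesis 1 concerns the change from baseline to 1 week post-treatment. The 209 comes from Aims 2 and 3. Hypotheses 2.1 and 2.2 are also worded as pre- to post-treatment changes, so only Aim 3 is worded as running to week 48: "Examine maintenance of treatment gains at 1-, 6-, 12-, 24-, and 48-weeks post-treatment". The stated Aim 1 requirement is 78; nothing here depends on whether that figure is right.
- **The size is trivial.** Two participants, or three recruits, are well inside the uncertainty of a guessed 10% attrition rate and a guessed slope variance.

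A reader might infer from 207 being below 209 that the plan misses its own 80% power. The documents do not support that. The 79.7% rests on assumptions that section 9.2 does not state, and on dropouts contributing nothing. On the same reconstruction, 230 complete participants give 83.7%; with partial data retained, power should lie between the two. The documents give no timing of drop-out, so it cannot be placed more exactly.

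None of this makes 230 a 10% allowance over 209. The plan chose to treat 209 as the number needed after losses, and on that basis the sentence is wrong.

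**Conclusion.** The stated attrition allowance is wrong in section 9.2 and in the synopsis. The target was inflated by multiplying by 1.10 instead of dividing by 0.90, so 230 allows for 21 losses (9.1%), and a full 10% allowance needs 233. This conclusion needs no assumption beyond reading attrition as a share of those recruited.

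The consequence is minor: two participants at week 48, bearing only on the figure derived for Aims 2 and 3. A loss of the planned 80% power is not shown, and neither is any effect on the co-primary analysis. This is a correction to a stated figure and gives no reason to change the design.

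**What to change.** Keep the target of 230. In section 9.2 and in the synopsis, restate the allowance: recruiting 230 retains the minimum of 209 with up to 21 losses, about 9% attrition from baseline to week 48; a full 10% allowance would require 233.

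Do not add a power figure for 207. It would rest on unstated inputs and would ignore the partial data that the planned analysis keeps.

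The cost is one sentence edited in two places, with a slightly less favourable stated allowance. No extra participants are needed, and section 4 and its enrolment table can stay as they are.

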9.3 Definition of Populations

Intention to Treat Analysis (ITT): We will include all randomized study participants who have at least baseline endpoint assessments in our ITT analysis. The ITT analysis is our primary method for assessing outcomes, and how it is performed will be determined based on the pattern of missingness. If the missingness is deemed MCAR, the LOCF method will be used: simply the most recent valid observation will be "carried forward" to replace the subsequent missing observations. If the missingness is deemed MAR, missing observations will remain as missing, and

maximum likelihood estimation, the default estimation algorithm of LMER, will be used to estimate these observations. If the missingness is found to be MNAR, multiple-imputed data will be used to construct LMER models.

Per-Protocol Analysis (PPA): For the PPA we will exclude study participants who: 1) fail to attend 13 out of 18 treatment sessions; 2) develop an exclusionary medical condition while on study protocol, or 3) receive interventions outside of the Allowed (Section 5.3.1) during treatment. Finally, we will assess how comparable estimated parameters vary between ITT and PPA analyses.

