6. STUDY PROCEDURES

6.1 Schedule of Evaluations

Assessment	Prescreen	Screen Visit 0	Enrollment & Baseline Visit 1	Treatment Visits 2-19	Post-Treatment Assessments Visit 20	Post-Treatment Assessments Visits 21-24
Numeric Pain Rating Scales 7-day & 24-hour	X	X	X	X*	X	X
Roland-Morris Disability Questionnaire	X	X	X		X	X
Fear Question	X	X				
Medical History - Back Pain	X	X				
Medication Log		X	X	X	X	X
Informed Consent Form		X				
Inclusion/Exclusion Criteria		X				
Enrollment/Randomization		X				
Medical History		X				
Physical Exam Form		X				
Adverse Events			X	X	X	X
Numeric Pain Rating Scale - Right Now			X	X	X	X
Standardized Reaching Paradigm • Pain & Harm Expectancy • Lumbar Spine Flexion			X	X*	X	X
Tampa Scale for Kinesiophobia			X		X	X
Center for Epidemiologic Studies - Depression			X		X	X
Pain Catastrophizing Scale			X		X	X
Pain Resilience Scale			X		X	X
Pain Self Efficacy Questionnaire			X		X	X
Brief Pain Inventory - Short Form			X		X	X
PROMIS-Anxiety			X		X	X
PROMIS-Depression			X		X	X
PROMIS-Positive Affect			X		X	X
PROMIS – Meaning and Purpose Scale			X		X	X
Life Fulfillment Scale			X		X	X
Profile of Mood States			X		X	X
Real World Activity Monitoring			X		X	X
Treatment Evaluation Inventory - Short Form			X		X	
Patient Global Impression of Change					X	X

*assessed at the first visit of each week

Note: Prescreening, Visit 0 screening, Visit 1 baseline, and Visit 2 first intervention can all occur on the same day.

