6.2.5 Completion/Final Evaluation

Assessments to be performed at the participant's final visit include:

- Numeric Pain Rating Scales 7-day & 24-hour
- Roland-Morris Disability Questionnaire
- Medication Log
- Adverse Events Log
- Numeric Pain Rating Scale – Right Now
- Standardized Reaching Paradigm (Pain & Harm Expectancy, Lumbar Spine Flexion)
- Tampa Scale for Kinesiophobia
- Center for Epidemiologic Studies – Depression
- Pain Catastrophizing Scale
- Pain Resilience Scale
- Pain Self Efficacy Questionnaire
- Brief Pain Inventory – Short Form
- PROMIS-Anxiety
- PROMIS-Depression
- PROMIS-Positive Affect
- PROMIS-Meaning and Purpose Scale
- Life Fulfillment Scale
- Profile of Mood States
- Real World Activity Monitoring
- Patient Global Impression of Change

All assessments will be performed for participants who discontinue study intervention early.

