9.5 Outcomes

9.5.1 Primary Outcome

The co-primary clinical outcomes are pain and disability, which will be assessed at pre-treatment baseline (visit 1) and at 1-, 6-, 12-, 24-, and 48-weeks post-treatment (i.e., visits 20-24).

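### Section 9.3 lets the observed missingness choose the primary ITT method, pairs LOCF with MCAR and unspecified multiple imputation with MNAR, and disagrees with Section 9.6

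*Combined protocol and SAP*

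**What the plan says.** Section 9.3 names ITT as the primary way of assessing outcomes and adds that "how it is performed will be determined based on the pattern of missingness". Three branches follow:

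- MCAR: "If the missingness is deemed MCAR, the LOCF method will be used", so the latest valid value fills every later gap.
- MAR: gaps are left as gaps and the mixed model is fitted by maximum likelihood.
- MNAR: "If the missingness is found to be MNAR, multiple-imputed data will be used to construct LMER models".

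No test, threshold or decision maker is given for assigning the data to a branch. No imputation model is given for the third.

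Section 9.6 specifies linear mixed-effects (LME) models for pain, disability, expectancy and flexion. It names LOCF as an example of an imputation strategy and states that "use of LME models to analyze longitudinal data renders these strategies largely unnecessary". Neither section says which one governs the primary analysis.

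Four other provisions bear on the size of the problem:

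- Section 9.2: "To allow for 10% attrition from baseline to 48-week follow-up, we will recruit 230 participants".
- Sections 6.1 and 9.5.1: after the Visit 1 baseline, the RMDQ is next scheduled at Visit 20.
- Pain is also rated during treatment. In Section 6.1 the 7-day and 24-hour scales are "assessed at the first visit of each week" and the right-now scale has no such limit; Section 6.2.4 lists all three at each treatment visit.
- Section 6.2.5: "All assessments will be performed for participants who discontinue study intervention early".

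**The concern.** A primary analysis should be one method, fixed in advance. Here two analysts could follow Section 9.3 faithfully, judge the missingness differently, and report different primary results for both co-primary outcomes.

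The pairings are also wrong. Under MCAR the likelihood LME is valid, so nothing is gained by switching to LOCF. LOCF assumes no change after the last observed value, whereas Hypothesis 1 is about change. A participant with neither a Visit 20 RMDQ nor an early-discontinuation assessment would be analysed as having zero change in disability.

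The MNAR branch cannot be carried out as written, because observed data cannot separate MAR from MNAR. If it were invoked anyway, multiple imputation with no stated departure from MAR would mainly repeat the MAR analysis. If dropout is related to outcome, nothing in the plan would reveal it. The per-protocol comparison concerns adherence and other protocol conditions, not missing outcomes.

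**Working it through.** **Inputs.** From Section 9.2: falls of 30% (experimental) and 10% (control), SD 75% of the mean, pre-post correlation 0.7, 10% attrition to week 48, N = 230. Results are in points, where 100 is the baseline mean; the true difference is 30 − 10 = 20.

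**The plan's attrition figure.** 209 × 1.10 = 229.9, which gives the stated 230. (Dividing instead, 209 / 0.90 = 232.2, would give 233; that small gap is not the point here.) The 10% runs to week 48, so loss before Visit 20 is an assumption. The range used is 10% / 5 post-treatment visits = 2%, an intermediate 5%, and 10% if all loss comes before Visit 20.

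**LOCF when MCAR is true.** With equal loss d and baseline carried forward, the estimated difference is 30(1 − d) − 10(1 − d) = 20(1 − d). This was checked by simulation: 115 per arm, 20,000 trials per setting, LOCF change-score t-test against a two-time-point likelihood estimate using all baselines. The range in the last column covers equal post-treatment SDs and SDs at 75% of each post-treatment mean.

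| Loss before Visit 20 | LOCF | Likelihood | Trials disagreeing on p < 0.05 |
|---|---|---|---|
| 2% | 20 × 0.98 = 19.6 | 20.0 | 2.0–2.2% |
| 5% | 20 × 0.95 = 19.0 | 20.0 | 3.0–4.0% |
| 10% | 20 × 0.90 = 18.0 | 20.0 | 4.7–6.3% |

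This holds for disability. For pain, if an on-treatment rating is carried forward and such ratings lie between the baseline and post-treatment means, the LOCF value falls between 20(1 − d) and 20.

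**LOCF when loss differs by arm.** Assume no true effect (both arms fall 30) and loss unrelated to outcome but 20% v 5%. LOCF gives a spurious difference of 30 × (0.20 − 0.05) = 4.5 points. Simulated type I error is 0.09 to 0.10, against about 0.05 for the observed-data analysis. Strictly, this missingness depends on arm, but Section 9.3 has no criterion that would keep it out of the LOCF branch. The 20% exceeds the planned attrition.

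**Multiple imputation under MNAR.** Assume experimental participants lost before Visit 20 had no change on average, and control losses are random. The true difference is 30(1 − d) − 10 = 20 − 30d.

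| Loss | Truth | Likelihood | MAR-based imputation |
|---|---|---|---|
| 2% | 20 − 0.6 = 19.4 | 20.0 | 20.0 |
| 10% | 20 − 3.0 = 17.0 | 20.0 | 20.0 |

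The imputation results use 20 imputations and 3,000 trials. A second simulation let experimental-arm dropout depend on the unseen outcome (about 10% v 7% missing). Imputation and likelihood both gave 24.1 against a true 20. In both cases the third branch returned the second branch's answer and missed the departure.

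**Section 9.3 against Section 9.6.** Section 9.3 makes LOCF the primary method in one branch; Section 9.6 regards LOCF as mostly needless once LME models are used. No sentence ranks the two.

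**The case against.** The strongest objection is about severity. At planned attrition the LOCF bias is small, and with equal loss it is towards no effect. Simulated power for LOCF and likelihood is 0.730 v 0.731 at 2% loss and 0.684 v 0.696 at 10%. The statistician is blinded until the end of the study (Section 9.2), so the branch can be chosen without knowledge of the arms. Sections 6.2.6 and 8 promise attempts to collect outcomes after any discontinuation, including the clinical measures when laboratory tests are refused. All this stands, and the case does not rest on the size of the LOCF bias. But blinding does not say which analysis is primary, and retention effort reduces loss without excluding it. Section 6.2.6 withdraws participants after a second sudden pain episode, and Section 5.1 asks for more lumbar motion in the experimental arm, so pain-related loss that differs by arm is plausible.

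On detail, the full 20(1 − d) shrinkage is established only for disability. In the first MNAR example LOCF would give 18.0 at 10% loss, nearer the true 17.0 than likelihood; that is because the example assumes the zero change that LOCF imposes, and it does not validate the method. Imputation using auxiliary treatment-visit data need not equal the LME exactly, but without a stated departure it still assumes MAR. Section 9.6 does not forbid LOCF, so the conflict is over which method governs.

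Finally, Section 9.6 leaves other parts of the primary model open, such as covariates chosen on baseline differences. That is a separate matter and does not excuse the rule in Section 9.3.

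**Conclusion.** The concern holds; Section 9.3 is wrong as written. The primary analysis of both co-primary outcomes is not one executable method. LOCF is assigned to the case in which the plan's own likelihood model is already valid, and the MNAR branch can be neither triggered from the data nor, without a stated departure from MAR, relied on to address MNAR. The MAR branch is sound.

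The numerical cost of LOCF for disability is 0.4 to 2.0 points of a 20-point difference, assuming the plan's effect sizes and equal random loss of 2% to 10% before Visit 20. For pain it is no larger, on the assumption stated for on-treatment ratings. At later visits LOCF bias can go either way, and no figure is claimed. Under the first MNAR illustration, dropout would overstate the effect by 0.6 to 3.0 points with no analysis in the plan to show it. The need for correction rests on the undefined primary method and the missing MNAR check, neither of which depends on attrition being high.

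**What to change.** Delete the three-way rule and its LOCF branch. State in both Sections 9.3 and 9.6 that the likelihood-based LME on all observed data, with missing values left missing, is the single primary ITT analysis for pain and disability.

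Replace the MNAR branch with a pre-specified sensitivity analysis for both co-primaries that departs explicitly from MAR. One option is delta-adjusted multiple imputation of Visit 20 values, with the imputation model and range of deltas stated and the tipping point reported.

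The drawback is that the primary analysis then relies on MAR, which is why the sensitivity analysis is needed. The cost is wording in two sections and one added analysis, with no new data. The change should be made before unblinding.
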